### **3.6. Subject Replacement**

Subjects who withdraw from the study will be replaced.

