##### *b. Study Visits and Procedures*

After the screening ultrasound confirms eligibility and a patient is given informed consent, the patient can then be randomized. If the patient is randomized to the intervention (detailed first trimester anatomy ultrasound), this scan is performed at the randomization visit if the patient is between 12w0d and 13w6d. If she is less than 12w0d, a separate study visit is scheduled for a date at her convenience during the days she is between 12w0d and 13w6d. A dedicated room and time slots have been made available for these study visits at Memorial Hermann Southwest and at the Fetal Center at UTPB. This separate scan/visit is not billed as it is not part of the standard of care.

After this detailed research ultrasound, which will be limited to 15 minutes, she then receives her clinically indicated dating ultrasound or nuchal translucency measurement. The total estimated time of all these ultrasounds is expected to be approximately 30 minutes, with breaks in between to allow the patient some movement and the opportunity to use the rest room, and to allow the exchange of operators (research staff vs clinical staff) and the creation of distinct records (research ultrasound is not saved to electronic medical records, so a new scanning encounter must be opened for the clinical ultrasound that day). The patient will complete a survey about her satisfaction with this technique via email. In addition, as a safety measure, if an anomaly is suspected on the day of the detailed first trimester anatomy scan, the patient will be unblinded. The research team will inform the clinical team so that a more detailed evaluation can be done and so that this information can enter the clinical record and affect clinical management.

Patients randomized to the intervention arm are later scheduled for a second trimester ultrasound by the clinical team, as this is part of standard obstetrical care. Research staff will ensure patients have this scan scheduled and completed, as it is part of study procedure. Data about this scan will be recorded in the patient's research record. This scan can be repeated as indicated according to UT's protocol for assessing anatomy.

If the patient is randomized to the comparison arm, she does not undergo a detailed first trimester ultrasound that day, but she does receive her clinically indicated limited ultrasound for dating or for nuchal translucency. She then undergoes a second

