trimester ultrasound by the clinical team as part of standard obstetrical care and completes a survey regarding her satisfaction with this technique via email. Research staff will ensure patients have this scan scheduled and completed, as it is part of study procedure. Data about this scan will be recorded in the patient's research record. This scan can be repeated as indicated according to UT's protocol for assessing anatomy.

*c. Final Study Visit:*

The final study visit is denoted by completion of the second trimester gold standard scan (GSS) for patients randomized to the intervention arm, and at the completion of the second trimester anatomy ultrasound for patients randomized to the comparison arm. Participants will continue to be followed through their pregnancy to document the number of ultrasounds required to complete the fetal anatomy evaluation.

*d. Post Study Follow up and Procedures*

Medical records will be reviewed after each study participant's due date to assess whether delivery has occurred and to record delivery outcomes from the medical records, when available. This is chiefly so that a post-natal evaluation can be recorded to confirm or exclude anatomical anomalies. Delivery outcomes are not a primary outcome and request of outside delivery records will not be required for a subject's record to be marked as completely collected.

Adverse outcomes, including discomfort during ultrasound as well as neonatal outcomes, will be recorded in the subject's research record.

*e. Discontinuation Visit and Procedures*

Subjects may withdraw voluntarily from participation in the study at any time. Subjects may also withdraw voluntarily from receiving the study intervention for any reason.

If a patient in the intervention arm withdraws from the study during to her first trimester anatomy ultrasound, she will be asked to complete the survey regarding her experience regardless of the duration of the first trimester ultrasound. She will then undergo her clinically indicated ultrasound (which are not transvaginal).

If a subject in the intervention arm withdraws from the study prior to her second trimester GSS ultrasound (done as "back up" for the intervention), a standard email will be sent to her confirming her withdrawal and encouraging her to seek a second trimester (standard of care) anatomy ultrasound as the anatomy evaluation she had in the first trimester is considered experimental.

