If a subject in the comparison arm withdraws from the study prior to her second trimester anatomy ultrasound, she will not be required to complete the survey about her experience. A standard email will be sent to her confirming her withdrawal and encouraging her to seek a second trimester (standard of care) anatomy ultrasound outside the study.

If voluntary withdrawal occurs, the subject will be given standard care under medical supervision until the symptoms of any adverse event resolve or the subject's condition becomes stable.

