## 6. BLINDING

Patients are not blinded to their group as they are aware of the timing of their detailed ultrasound. The clinical team will not be informed of the patient's randomization assignment, images from research ultrasounds will not be available to the clinical team, and the clinical team will not be made aware of whether the second trimester scan done by them is for comparison to the gold standard (the GSS in intervention arm patients) or for anatomy (in comparison arm patients).

Patients and the care team will be unblended from the results of the first trimester exam if there is an anomaly. There are no other plans for unblinding.

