**Withdrawal Email 1 (for intervention arm, withdrawing during her detailed first trimester ultrasound)**

Dear [Name],

We are sorry to see you go! Thank you for considering EASE-O, a randomized clinical trial to find out when is the best time for a detailed anatomy ultrasound in women with a BMI of 35 or greater. This email confirms that you have withdrawn from the study. Your data will not be analyzed and no further data will be collected.

You do not have to do anything further, but we ask that you tell us about your experience during your ultrasound, at [this link](#). Filling out this survey helps us understand what women like you prefer regarding their ultrasounds. We want to hear from you!

Sincerely,

[name]  
Principle Investigator, EASE-O

**Withdrawal Email 2 (for intervention arm, withdrawing after her detailed first trimester ultrasound, before her safety second trimester ultrasound)**

Dear [Name],

We are sorry to see you go! Thank you for participating in EASE-O, a randomized clinical trial to find out when is the best time for a detailed anatomy ultrasound in women

with a BMI of 35 or greater. This email confirms that you have withdrawn from the study. Your data will not be analyzed and no further data will be collected.

You do not have to do anything further, but we encourage you to seek out an ultrasound between 18 and 22 weeks gestational age, if you haven't already gotten one. You did have an ultrasound in the first trimester looking at all the baby's parts, but these ultrasounds are still considered experimental (that's why we are researching them)! You deserve a later ultrasound, it is still recommended and will be covered by your insurance as part of your routine prenatal care.

Sincerely,

[name]  
Principle Investigator, EASE-O

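### Withdrawal Email 1 leaves out the advice to have an 18 to 22 week anatomy scan that Emails 2 and 3 give, and section 4.3.e does not make clear whether that was intended

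*Combined protocol and SAP*

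**What the plan says.** Section 4.3.e of the protocol (Discontinuation Visit and Procedures) describes three specific withdrawal situations.

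- **Intervention arm, during the first trimester research scan.** A woman who "withdraws from the study during to her first trimester anatomy ultrasound, she will be asked to complete the survey regarding her experience" then goes on to her clinically indicated ultrasound. The paragraph mentions neither an email nor a later anatomy scan.
- **Intervention arm, before the GSS.** The rule begins "If a subject in the intervention arm withdraws from the study prior to her second trimester GSS ultrasound". It provides for a standard email that confirms the withdrawal, "encouraging her to seek a second trimester (standard of care) anatomy ultrasound as the anatomy evaluation she had in the first trimester is considered experimental".
- **Comparison arm, before the second trimester anatomy scan.** The standard email again confirms the withdrawal, "encouraging her to seek a second trimester (standard of care) anatomy ultrasound outside the study".

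The standardized emails appendix has three withdrawal templates. Email 1 is for withdrawal during the first trimester scan. It confirms the withdrawal and continues "You do not have to do anything further, but we ask that you tell us about your experience during your ultrasound", followed by the survey link. Email 2 is headed for the intervention arm after the first trimester scan and before the second trimester one. Email 3 is for the comparison arm before its second trimester scan. Both encourage an ultrasound between 18 and 22 weeks.

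**The concern.** The plan treats the second trimester scan as the safeguard for women whose anatomy was examined experimentally. The intervention-arm reminder email describes it as a safety measure. A woman who leaves partway through the research scan has at most a partial experimental examination, plus a clinical scan for dating or nuchal translucency. The one withdrawal message written for her says that nothing more is required and does not point her to the later scan. If it is sent as written, she is the only one of the three groups with a withdrawal template who does not get that advice. What is at stake is patient communication and a small element of safety. No estimate or error rate is involved.

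**Working it through.** The plan states no figure on this point and no formula applies. The check is a comparison of texts.

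**1. Protocol paragraph against email template**

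| Withdrawal situation | Advice in 4.3.e paragraph | Template | Advice in template |
|---|---|---|---|
| Intervention arm, mid-scan | Silent | Email 1 | No |
| Intervention arm, before GSS | Yes | Email 2 | Yes |
| Comparison arm, before second trimester scan | Yes | Email 3 | Yes |

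The advice appears in 2 of 3 paragraphs and 2 of 3 templates. The mid-scan row is the exception in both.

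**2. Does the pre-GSS rule reach the mid-scan woman?** Taken literally, yes. The research scan takes place at 12w0d to 13w6d and the GSS at 18w0d to 22w6d, so anyone who withdraws during the first has withdrawn before the second. The rule has no words limiting it to completed scans, and the mid-scan paragraph contains no exemption from it.

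**3. Is there evidence for a narrower scope?** Yes, in three places. The rule's stated reason refers to a first trimester evaluation that the woman has already had. The heading of Email 2, which implements the rule, is restricted to withdrawal after that scan. The three paragraphs also match the three templates one to one, which suggests that they were drafted as separate cases. The text does not settle which reading was meant.

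**4. Does another withdrawal template give her the advice?** No. Email 2's heading excludes her and Email 3 is for the other arm. This holds on either reading of 4.3.e.

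**5. Is there a reason to treat her differently?** None is given. Email 3 advises comparison-arm women on the ground that their first trimester scan did not examine the whole baby. Email 2 advises women who may have completed the research scan. The mid-scan woman's need is at least as great as that of the Email 2 group.

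**6. What else would bring her to the later scan?** Section 4.3.b says that intervention-arm patients are "later scheduled for a second trimester ultrasound by the clinical team, as this is part of standard obstetrical care". Section 6 says that "images from research ultrasounds will not be available to the clinical team", so a withdrawal gives that team no reason to drop the scan. The Welcome Email also mentions an ultrasound between 18 and 22 weeks, although the plan does not say when that email is sent. Two other supports are less certain. Research staff check that the scan is scheduled and done because it belongs to study procedure, and the reminder email is written for women still in the study. The documents do not say that either continues after withdrawal.

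**7. How many women?** No number is given. The minimum is 0. The planned arm size, 118 / 2 = 59, is not a ceiling, because section 3.6 states "Subjects who withdraw from the study will be replaced", so more than 59 could be randomized to the intervention. Under section 7.2, a scan stopped for discomfort is still assessed for completion on the images obtained, so stopping the scan is not in itself withdrawal.

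**The case against.** The strongest reply is that there is no conflict. The mid-scan case has its own paragraph in 4.3.e, a specific provision normally governs its own case, and Email 1 delivers what that paragraph asks for: the survey. The pre-GSS rule can then be read as addressed to women who have had the first trimester evaluation. This reply has real weight. A reader might infer that Email 1 flatly contradicts 4.3.e, and the documents do not support that, because both readings are open. The reply does not remove the gap, since on the narrower reading the advice is missing from the protocol paragraph as well as from the template.

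A second reply is that routine care makes the email unimportant. The second trimester scan does not depend on study emails. A woman who knows she stopped the scan may also be less exposed to false reassurance than one who finished it. This limits the consequence, and it stands to that extent. It does not explain the omission, because the same routine care covers the recipients of Emails 2 and 3, and the plan advises them anyway.

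A reader might also infer that these women are never told about the later scan, or would miss it. The documents do not support that either. The Welcome Email mentions it, the clinical team schedules it, and the consent form is not in the copy reviewed and so cannot be checked.

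**Conclusion.** The point holds as a minor drafting gap. Email 1 omits advice that the other two withdrawal templates give, and 4.3.e is ambiguous about whether a woman withdrawing mid-scan should receive it. The claim is confined to what this email and the mid-scan paragraph say. It assumes that the templates would be sent as written. The expected effect on care is small, the number of women affected may be zero, and no upper bound can be computed from the documents.

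**What to change.** Add to Email 1, after the confirmation of withdrawal, wording such as: *Please plan to have an anatomy ultrasound at 18 to 22 weeks. The research scan you began with us is experimental and was not completed, so it should not take the place of that check. The later scan is still recommended as routine prenatal care.* Email 2's text should not be pasted in unchanged, because it describes a scan that looked at all of the baby's parts, which may be untrue after an interrupted one.

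Add a sentence to the mid-scan paragraph of 4.3.e stating that she will be emailed confirmation of her withdrawal together with the same advice. On the literal reading of the pre-GSS rule this is a clarification. On the narrower reading it is a small new commitment. Either way it removes the ambiguity.

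The cost is one revised template and one protocol sentence, submitted to the IRB. Sample size, outcomes and analysis are unaffected.

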**Withdrawal Email 3 (for comparison arm, withdrawing from study before detailed second trimester ultrasound)**

Dear [Name],

We are sorry to see you go! Thank you for participating in EASE-O, a randomized clinical trial to find out when is the best time for a detailed anatomy ultrasound in women with a BMI of 35 or greater. This email confirms that you have withdrawn from the study. Your data will not be analyzed and no further data will be collected.

You do not have to do anything further, but we encourage you to seek out an ultrasound between 18 and 22 weeks gestational age, if you haven't already gotten one. The ultrasound you got in the first trimester was only to establish the dating of your pregnancy or check on the back of the baby's neck, and didn't look at all the baby's body parts. A detailed ultrasound between 18 and 22 weeks recommended and will be covered by your insurance as part of your routine prenatal care.

Sincerely,

[name]  
Principle Investigator, EASE-O

## APPENDIX 4

[figure not shown]
### First Trimester Anatomy Ultrasound Protocol

#### Initial survey:

[figure not shown]
[figure not shown]
1. Document location of an intrauterine gestational sac (confirm not in prior hysterotomy or uterine isthmus)
2. Document cardiac activity using M-mode
3. Document fetal number and chorionicity if applicable
4. Document placental position in relation to the cervical os (most previas are of no clinical significance)
5. Document any subchorionic hemorrhage
6. Biometry:
  - a. Document CRL or
  - b. Document HC, AC, BPD, and FL if greater than 11 weeks

#### Planes:

[figure not shown]
[figure not shown]
1. **Midsagittal fetus.** Landmarks required for optimal image: NT, nose, cord insertion, bladder
2. **Profile.** Landmarks required for optimal image: NT, nasal bone, maxilla

[figure not shown]
[figure not shown]
3. **Transventricular plane.** Landmarks required: bilateral symmetrical choroid plexus.
4. **Transthalamic plane.** Landmarks required: bilateral thalami, falx cerebri between anterior horns of the lateral ventricle.

[figure not shown]
[figure not shown]
5. **Transcerebellar plane.** Required landmarks: bilateral thalami, fourth ventricle.

[figure not shown]
6. **Orbital plane.** Required landmarks: bilateral orbits.

[figure not shown]
7. **Facial plane.** Required landmarks: bilateral orbits, bilateral maxillary processes.

[figure not shown]
[figure not shown]
[figure not shown]
8. **Four chamber view.** Required landmarks: two ventricles, two atria in diastole.

[figure not shown]
9. **Three-vessel-trachea view.** Required landmarks: V-shaped aorta/PA with same directional flow, trachea.

[figure not shown]
[figure not shown]
[figure not shown]
10. **Coronal trunk.** Required landmarks: stomach/diaphragm.  
11. **Retroperitoneum.** Required landmarks: bilateral kidneys

12. **AC.** Required landmarks: stomach, umbilical vein.
13. **Cord insert.** Required landmarks: cord insertion with abdominal skin away from adjacent tissue
14. **3VC.** Required landmarks: bladder, bilateral umbilical arteries using Doppler.

[figure not shown]
[figure not shown]

15. **Extremities.** Can be captured by imaging bilateral arms/hands, then bilateral legs/feet, or by imaging the right extremities together and the left extremities together. Required landmarks: four upper and four lower limbs. Can also be captured in 3D. (Fingers and toes not required.)

16. **Spine.** Required landmarks: entire spine with overlying skin not adjacent to any other structures.

**Additional planes:**

1. Assess maternal anatomy

2. Assess prior hysterotomy if applicable
3. Obtain uterine artery doppler measurements
4. Obtains subtraction imaging of amniotic fluid volume
